## Study Protocol:

### Objectives:

This research project aims to develop and test a Student Stress Management (SSM) mobile program, a suite of apps based within the framework of an evidence-based treatment for depression and anxiety that will be integrated within a student health system. This program will improve engagement with mental health services by serving as an access point to mental health treatment options, and providing an opportunity for self-guided treatment. The SSM program will feature components known to be effective both for engagement (symptom assessment and promotion of care accessibility) and treatment (thought restructuring, relaxation exercises, and behavioral activation). Within the suite, students will be prompted to complete symptom assessments on a weekly basis, and those with elevated symptom scores will be provided with feedback and recommendations for on-campus services. All users will be able to access and use interactive treatment apps. The program will be developed with the University of Illinois at Chicago (UIC) and Northern Illinois University (NIU) counseling centers, and will be made available to all UIC and NIU students. These studies will establish a research program that will expand the reach of services and ease the burden of untreated depression and anxiety for college students.

**Phase 1 Aim: Develop the SSM program by refining a mobile smartphone intervention and develop an optimized multi-component implementation strategy using a user-centered design process.** We will start from a suite of apps developed for a general population and, based on needs reported by current students and mental health care providers, they will be optimized for the college student population alongside development of an implementation plan and evaluation metrics. Laboratory-based usability testing and an 8-week field trial will be included as part of the iterative design process to ensure that SSM works optimally both in individual interactions, as well as cumulatively over time.

**Phase 2 Aim: Conduct a trial of the SSM program within two university communities.** The overall aim of this study is to pilot the SSM program, evaluation metrics, implementation strategies, data collection and assessment procedures for a larger implementation trial. Counseling center utilization will be measured for one academic year to obtain a baseline for both sites. One site will be randomly selected and the SSM program will be implemented, while the other site will continue to collect baseline data. After one academic semester, the additional implementation strategies will be incorporated for an enhanced implementation plan, and both study sites will receive the enhanced implementation plan for one semester. During the implementation phases, counseling center utilization and SSM program use, will be tracked.

**Hypothesis 1:** Introduction of the SSM program will impact utilization of counseling center resources, and the use of an enhanced implementation plan will increase program penetration (e.g., app downloads) and strengthen its impact on utilization. We will explore multiple metrics to assess program impact on utilization, and hypothesize the number of appointments for crisis and follow-up will 1) be reduced during implementation relative to pre-implementation and 2) will be reduced in enhanced implementation relative to initial implementation. We will also explore the impact of implementation on seasonal variations in

counseling center utilization, level of depressive symptoms (as measured by the PHQ-9) at intake, and any other evaluation metrics identified during Phase 1.

**Hypothesis 2:** Sustained use of the SSM program will result in reductions in depression and anxiety among individual users, and these reductions will be mediated by increases in mental health literacy, knowledge of mental health care services, and cognitive and behavioral coping skills.

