### **Procedures Involved:**

Monthly data on engagement with counseling center services will be collected from the counseling center’s Titanium Electronic Medical Record (EMR) to serve as a predeployment “baseline” for Phase 2. For the primary outcome of counseling center resource utilization, we will compare the predeployment phase (the 2 semesters prior to program implementation) to the implementation phases. During the predeployment phase, weekly data will be collected from existing service records at the counseling centers at UIC and NIU on new counseling appointments, follow-up appointment, group therapy appointments and crisis appointments. The data will be reported in aggregate and will not include individual personal identifiers. The SSM program will first be implemented in one study site (UIC or NIU – chosen via random selection) using the initial implementation plan (e.g. advertisements, identification of early adopters, identification of student leaders to serve as champions) designed in Phase 1. Data from individual interviews will be gathered from the first study site will inform an enhanced implementation plan. During this third semester, predeployment data will also be collected at Site #2. Then, the enhanced implementation plan, updated based on the semester 3 deployment at Site #1, will be deployed at both study sites and data will be collected for an additional semester. When the implementation begins on each campus, the program will be made freely available to download, and counseling center intake paperwork will be modified to ask students if they used the SSM program which allows for tracking of counseling center referrals while maintaining patient confidentiality. This design allows us to examine: a predeployment phase for both sites, an initial phase of implementation for Site #1, and an enhanced implementation phase for Site #1 and for Site #2. A strength of this implementation design is that it allows for learning within itself by comparing initial implementation strategies with an enhanced implementation plan. This process of learning and adapting is key for effective and sustainable implementation. Staggering the start times of implementation allows for within-site targeted comparisons of effect of introducing the SSM program on utilization of the counseling center in each site, and for an exploration of between-site differences in the impact of the enhanced implementation plan.

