The study utilizes an interrupted time-series design, which offers a number of benefits over large-N designs and has been shown to be an acceptable approach for examining treatment efficacy as well as a useful design for rigorous implementation research when few sites are

involved. There are both scientific and pragmatic benefits to introducing a program into a system with this design approach. Since these time-series measurements are recorded on a weekly basis, one can observe how change unfolds across time, examine seasonal effects to better evaluate change in these centers that are often at capacity, and investigate the trajectory of change. Because all members of the campus community are granted access to the program, this design meets the needs of community stakeholders.

To examine outcomes for Hypothesis 2 (sustained use of the SSM program will result in reductions in depression and anxiety among individual users, and will be mediated by increases in mental health literacy, knowledge of mental health care services, and cognitive and behavioral coping skills), we will examine longitudinal data from individual users regarding depression and anxiety symptoms, mental health literacy, knowledge and beliefs about mental health care services, barriers to mental health care, and cognitive and behavioral coping skills to determine if sustained program use is associated with changes in these measures.

*SSM Program:* The program will prompt users to complete repeated symptom assessments and provide psychoeducation regarding current symptoms while encouraging students in need to utilize available campus services. Upon download, the Student Hub app will prompt users to complete the PHQ-8 and GAD-7 and will provide feedback on symptoms. Based on symptom scores, users will receive automated feedback about depression/anxiety, availability of mental health and wellness services on campus, and information and interactive digital tools to support continued stress management and wellness. Users will be prompted with ability to use interactive self-help tools within the app suite. Interactive, clinical apps (designed for daily use) are included to facilitate engagement with mood monitoring, and to appeal to a preference for self-reliance.

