**Statistical Analysis Plan:**

We used a mixed-methods approach to analyzing the impact of the IntelliCare for College Students program, in that we analyzed quantitative data on app usage and counseling center utilization alongside qualitative data generated through interviews with students and staff.

Demographic data were examined primarily in the form of descriptive statistics, and chi-square tests and a student's t-test were used to examine potential demographic differences between the participants who consented to the study that did (n=117) and did not (n=65) download and register their participant ID to the IntelliCare for College Students app. App usage data were examined in the form of descriptive statistics.

Due to missing data throughout the trial, multiple imputation methods and separate generalized linear mixed models to account for repeated measures from each participant over time, were used to examine symptoms of depression and anxiety at baseline, week 1, week 2, week 4, week 6 and week 8, and anxiety literacy, depression literacy, and cognitive and behavioral coping skills at baseline, month 1 and month 2.

To examine symptom assessments longitudinally, we fit the available weekly symptom assessment data into a structure of baseline, week 1, week 2, week 4, week 6 and week 8 timepoints. Only 2 individuals had complete data. A total of 48 participants only completed the symptom assessment at one time period, 16 (17) completed 2 of the 6 assessments (16 for GAD, 17 for PHQ), 3 (2) completed 3 of the 6 assessments, 5 had 4 of the 6 assessments, and 5 were missing just one assessment. Multiple imputation methods were used to account for missing data. Participants were also prompted to complete measures of our mental health intervention targets on a monthly basis within the app. Many participants did not complete these assessments, and data were examined at baseline, month 1, and month 2. Multiple imputation methods were used to account for missing data.

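### Hypothesis 2 claims that app use causes symptom reduction, but the SAP examines only uncontrolled change among users from a score taken at download.

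*Combined protocol and SAP*

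**What the plan says.** - **The hypothesis (Objectives, Phase 2 Aim).** "Sustained use of the SSM program will result in reductions in depression and anxiety among individual users". This is a causal statement about individuals.
- **The data (Procedures Involved).** The source is users only: "we will examine longitudinal data from individual users regarding depression and anxiety symptoms". The stated purpose is softer than the hypothesis: "to determine if sustained program use is associated with changes in these measures". Sustained use is not defined.
- **The first score (Procedures Involved, SSM Program).** "Upon download, the Student Hub app will prompt users to complete the PHQ-8 and GAD-7". The student decides when that happens.
- **Access (Procedures Involved).** The app is open to everyone on a campus once implementation starts there, as a deliberate choice for stakeholders: "Because all members of the campus community are granted access to the program". No individual-level control group is described.
- **The model (Statistical Analysis Plan).** Scores are arranged on a time-since-start grid: "we fit the available weekly symptom assessment data into a structure of baseline, week 1, week 2, week 4, week 6 and week 8 timepoints". They are then analysed, after multiple imputation, with "separate generalized linear mixed models to account for repeated measures from each participant over time". No comparator, usage measure or calendar variable is named.
- **Where the design does have comparisons (Procedures Involved).** The staggered start supports "within-site targeted comparisons of effect of introducing the SSM program on utilization of the counseling center in each site", which belongs to Hypothesis 1.

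**The concern.** Three things can lower or raise a user's score over eight weeks: the app, a return towards that person's usual level after an unrepresentative first score, and whatever is happening on campus at the time. With users only, a self-chosen start and time since start as the only named time scale, the described analysis cannot tell these apart.

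The bias could go either way. If students tend to download when they feel worse than usual, scores would fall without any help from the app. If most start early in a semester and distress then rises, a real benefit could be hidden. In either case a causal conclusion on Hypothesis 2 would rest on an analysis that cannot support it, and Phase 2 is meant to prepare a larger implementation trial into which that conclusion could be carried.

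**Working it through.** The documents give no effect size, SD, retest correlation, alpha or sample size for Hypothesis 2, so there is no planned figure to reproduce. The check has three parts.

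**1. Does any part of the plan identify an app effect on individual symptoms?**

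- *Predeployment phase and staggered sites.* These serve counseling center utilization, analysed by Simulation Modeling Analysis in the SAP. Hypothesis 1 also plans to explore PHQ-9 level at counseling intake. That concerns students attending the center and is not a comparator for app users.
- *Seasonal analysis.* It is described for center utilization and capacity. None is described for individual symptom scores.
- *Consented students who did not register in the app (65, against 117 who did).* They are compared on demographics only.
- *Association of use with change.* It is stated in Procedures Involved, but no such analysis is named in the SAP. If it were run, use would be self-selected. Students who improve for other reasons may use the app more or less, so the association would not isolate its effect.

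None of these routes identifies the effect.

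**2. How large could a fall be with no app effect? (Illustration only.)**

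Expected fall = (1 − r) × (mean first score − mean to which scores return), where r is the retest correlation. Both inputs are assumptions: an elevation of 2 to 4 points and r of 0.6 to 0.8.

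- Smallest: (1 − 0.8) × 2 = 0.4 points.
- Largest: (1 − 0.6) × 4 = 1.6 points.

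To see what this does to a test, take a two-sided 5% paired z-test with equal variances. The SD of change is √(2(1 − r)) SD. With r = 0.6 and a first score 0.5 SD high:

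- Fall = 0.5 × 0.4 = 0.20 SD; SD of change = √0.8 = 0.894 SD; ratio = 0.224.
- n = 31: 0.224 × √31 = 1.24, so a significant result occurs about 24% of the time.
- n = 79: 0.224 × √79 = 1.99, so about 51% of the time.

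Over r from 0.5 to 0.8 and an elevation of 0.25 to 0.75 SD, the ranges are 7% to 55% (n = 31) and 11% to 92% (n = 79), against a nominal 5%. This is a simpler test than the imputed mixed model in the SAP. It shows the mechanism and does not predict this trial's result.

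**3. How much data could support an adjusted analysis?**

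Counts from the SAP, by number of assessments completed (1, 2, 3, 4, 5, 6):

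- GAD: 48 + 16 + 3 + 5 + 5 + 2 = 79.
- PHQ: 48 + 17 + 2 + 5 + 5 + 2 = 79.
- Two or more assessments: 79 − 48 = 31, which is 39% of 79 and 26% of the 117 registrants.
- Scores observed: GAD 48 + 32 + 9 + 20 + 25 + 12 = 146; PHQ 48 + 34 + 6 + 20 + 25 + 12 = 145. Out of 79 × 6 = 474 slots, about 69% are empty.

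The SAP does not say which weeks were completed. Only the 2 participants with complete data are certain to have both a week 1 and a week 8 score; the number cannot exceed 31.

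**The case against.** The strongest reply has four parts.

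- **The protocol is already associational in one place.** Procedures Involved speaks of association, and the SAP says only that symptoms were examined; it claims no app effect. This stands in part. A reader might infer that the plan already reports the change as an app effect, and it does not. But the causal hypothesis remains the stated objective, and the associational analysis is missing from the SAP.
- **Downloaders need not be at a symptom peak.** A reader might infer that the first score is taken just after a student seeks help. The documents do not say so: Study-Wide Recruitment Methods relies on e-mail, posters, digital signage and social media, and Phase 2 has no symptom threshold. This stands. Regression to the mean is a plausible threat here, not an established one.
- **Semester-linked symptom change is not documented.** Background mentions academic pressure and seasonal variation in center capacity, not symptom swings within a term. The SAP lists no covariates at all, so one can say only that no calendar term is named. This stands as a limit on how firmly the threat can be put.
- **This is a pilot with deliberate open access.** That is a fair reason for having no control group. It is no reason for a causal conclusion.

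**Conclusion.** The concern holds in a limited form. The causal wording of Hypothesis 2 is not supported by the analysis in the SAP, and no other element of the plan identifies an app effect on users' symptoms. That conclusion needs no numerical assumption.

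The size and direction of any bias cannot be derived from the documents. The 0.4 to 1.6 point fall rests wholly on the assumed elevation and retest correlation. A reader might infer a larger figure by treating the 20% moderate-severe share in Background as the share scoring 10 or more. With normal scores and an SD of 4 to 6, that group lies about 1.40 SD above the mean, and 1.40 × 4 × 0.2 to 1.40 × 6 × 0.4 gives 1.1 to 3.4 points. That figure does not apply here: Background states no cut-off, Phase 2 does not select on score, and the SAP describes no such subgroup.

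**What to change.** **Main change.** Bring the Hypothesis 2 conclusion into line with the associational aim in Procedures Involved. Report change in symptoms among users over eight weeks and, if it is analysed, its association with a defined measure of use. State that this does not show that use caused the change. Because the SAP is written in the past tense, the change should limit the conclusion and leave the hypothesis on record as stated.

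**Sensitivity analyses only.**

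- If the date of each score is available and start dates vary enough to separate time since download from time in semester, add campus and a parsimonious time-in-semester term to the mixed models. If starts cluster, the two time scales will be nearly collinear, and that should be reported.
- Show the week 1 to week 8 change beside the baseline to week 8 change. Regression from an unusual first score may occur largely by the first retest. This contrast also discards any true first-week benefit, so it should not replace the main estimate.

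**Cost.** The rewording costs only a more modest claim. The sensitivity estimates will be imprecise and will lean heavily on imputation, given 31 of 79 scored participants with two or more assessments. Neither analysis creates a control group, so neither can restore the causal claim.

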**Background:**

College student mental health problems. With rising rates of students demonstrating clinically significant symptoms of depression and anxiety, there has been a broadly recognized college student mental health crisis in recent years. As students face increased stress and academic pressures, 85% of college students report feeling overwhelmed by demands over the last year. In a national survey of college students, 20% screened positive for moderate-severe depressive symptoms, and 20% screened positive for moderate-severe anxiety symptoms. However, many students have low mental health literacy as they do not recognize a need for treatment, believing that these depression and anxiety symptoms are typical college stress. As nearly 70% of Americans enroll in college following high school (and even more in subsequent years), this is an important point for intervention. At this life phase, untreated mental illness can have life-long impacts, including increased risk of substance use, academic failure, and impaired relationships. Untreated depression is the number one cause of suicide, which is the second leading cause of death for this age group.

Insufficient access to mental health resources for college students. While many students do not recognize a need for treatment, students who do recognize a need often endorse difficulties accessing care, perceive care available as inconvenient, and are skeptical about the efficacy of care. Campus counseling centers are well-positioned to provide mental health care. For many students, particularly those from low-income backgrounds without access to a parent's insurance plan, these centers are the main option for affordable care. However, many counseling centers across the country are under-resourced, have difficulty reaching students in need of treatment, and while there are seasonal variations in capacity, are at full capacity during much of the year. Students are increasingly being seen in crisis, rather than when symptoms are moderate. Over the last 6 years, rates of students presenting to these clinics with symptoms of depression and anxiety trended upward, and utilization of crisis services have increased by 28%. ***There is a clear, immediate need to develop accessible methods for delivering effective mental health care to college students.***

Need for alternative methods of care delivery Developing accessible and effective interventions could facilitate early management and treatment of symptoms – saving many individuals from the detrimental impact of untreated mental illness including social, emotional, and financial costs. Behavioral intervention technologies (BITs), including smartphone apps, offer the possibility to expand treatment options and to reduce barriers to services. Internet-based CBT has demonstrated efficacy for treating a wide range of mental health concerns, and self-guided treatments are known to be effective for treating common mental health problems such as depression. Early work suggests that programs delivered via mobile phone are comparably efficacious while circumventing some barriers to computer-based treatments. As smartphones are often carried throughout the day, apps provide access in the real-world conditions of

individuals with mental health concerns. Thus making apps an accessible method for delivering mental health care to students, which could keep students with lower levels of distress well-managed and not in need of counseling center appointments.

**Potential in Mental Health Apps** Commercially available mental health apps have been rapidly emerging over recent years, and demand for them is high. In the U.S., 85% of 18-29 years olds own a smartphone, and more than 75% of Americans are interested in free mobile apps aimed at mental health management and treatment. While interest exists, few existing apps have been subject to empirical evaluation, fewer have demonstrated clinical efficacy, and those that demonstrated efficacy are typically not available to the general public. Appropriate mental health apps are challenging for individuals to locate, leading users to face significant barriers to find something trustworthy and useful. Empirically tested app-based programs are needed to fully realize the promise and potential for their use in clinical care.

**Mental Health Technologies for College Students.** College students are ideal candidates for mental health technologies. Research on mental health help-seeking in young adults has identified a preference for self-reliance and low mental health literacy, resulting in a failure to recognize symptoms as signs of treatable mental health conditions, as the most important barriers to seeking care. These barriers are a toxic combination but are prime targets in which BITs can facilitate mental healthcare. By providing a program that includes self-guided treatment, we can appeal to a preference for self-reliance and facilitate program engagement to promote mental health literacy and provide further referrals when students need services. A recent RCT of a web-based suicide risk screening program for college students found that the provision of personalized feedback, with the option of online counseling based on motivational interviewing, had a significant impact on students' readiness to consider mental health treatment, and these students were more likely to link up with mental health services.

However, there were relatively low levels of engagement with the site, and authors noted the site's subpar user interface likely contributed to low utilization by students.

BITs for college students need to be strategically designed to promote use. College students today are digital natives confident about their ability to access and navigate digital interfaces, and, counter to older adults, tend to view usability issues as the fault of the program or website. There are challenges in engaging these users to continue to interact with new technologies. Young adults are seen to exhibit distinct preferences in interface design relative to both teenagers and older adults, and they are quick to dismiss tools that do not meet their expectations. In the general population, 1 of 5 apps downloaded are only used once. The risks of BIT rejection/non-use are greater among young adults, and can likely be prevented with appropriate design. User centered design processes and usability testing, widely used methods from the field of Human-Computer Interaction (HCI), are vitally important to develop usable, useful programs. Once developed, it can be a challenge to get these programs into the hands of people who could benefit from them. Thus, implementation plans must be carefully developed and iterated upon as necessary. Implementation scientists have outlined 73 discrete implementation strategies; however, use of a single strategy is rare and a multicomponent implementation plans are typically developed to address multiple barriers within a system. Identification of implementation strategies likely to be successful in a setting is key to program success.

To evaluate the needs and preferences of college students seeking digital mental health resources, I conducted a pilot study of an internet-based cognitive-behavioral therapy (iCBT) program with 15 college students and collected user feedback. The iCBT program was rated usable and useful, with an average of 12 logins over the 6-week trial period (range: 2–35 logins), and nearly three-quarters of participants indicated that they would recommend it to a friend. From baseline to end of treatment, students reported an increase in use of cognitive-behavioral coping strategies,  $t(10)=3.40, p=.007$ , and a trend was observed for decreased levels of stress,  $t(11)=2.12, p=.058$ . However, many students reported that making time to be in front of a computer was a barrier to program use. A majority reported interest in app-based programs, noting a greater likelihood of frequently utilizing program content and tools if easily accessible on their phones. Based on these data, the proposed project will use smartphone apps to deliver program content and tools.

Apps used in this study are drawn from IntelliCare and will be optimized based on feedback from participants in Phase 1. IntelliCare is a suite of clinical apps, developed at CBITs, that feature different methods of managing mental health. To fit with standard app use patterns, the apps are lightweight and designed to be used in short bursts of time. In conjunction with ongoing trials, the IntelliCare apps were made freely available. In the first 18 months of public availability, 8,293 individuals downloaded one or more of the apps, for a total of 19,852 downloads.

